4.2 ELIGIBILITY

Inclusion criteria:

- 1. Women pregnant or within 6 weeks of the end of the pregnancy.
- 2. Women with a suspected or confirmed infection requiring in-patient care:
 - A. Any suspected or confirmed infection with or without organ-dysfunction.
 - B. Any clinical signs suggestive of infection (e.g., fever).
 - C. Request for any bodily fluid culture (blood, urine, cerebrospinal fluid, etc.) or swab specimens (nasopharyngeal, oropharyngeal, vaginal, endocervical) for the diagnosis of suspected infection (not routine sampling e.g., routine COVID-19 screening).
 - D. Non-prophylactic use of antibiotics or other antimicrobial drugs at admission or during hospital stay.
 - E. Any procedure for treatment of a suspected infection (e.g., wound exploration, evacuation of the uterus, laparotomy, etc.).
 - F. Any unexplained organ-dysfunction (i.e., organ dysfunction not attributable to an underlying cause).
- 3. Estimated age \geq 16 years.
- 4. Willing to provide a signed (and witnessed, if applicable) informed consent form.

- 5. Willing to be contacted if necessary.
- 6. Willing to have additional blood samples taken.

Exclusion criteria:

- 1. Women In active labour or within 2 hours of delivery are excluded as lactate is expected to be elevated by labour and childbirth.
- 2. Women with any non-severe, localised, or chronic infection (TB, HIV) or colonization (GBS).
- 3. Women undergoing only treatment with prophylactic antibiotics (for procedures, GBS).

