5.3 REFERENCE STANDARDS

The reference standard for diagnosis of maternal sepsis is defined by Sepsis-3 criteria (3): women with both (i) suspected maternal infection and (ii) organ dysfunction, which will be identified by a SOFA score ≥2. Maternal sepsis will be assessed at Day 0 (sample 1) and Day 1 (sample 2) (22-36 hours after sample 1 is taken). Women will be diagnosed as having sepsis if they meet the criteria at either time point. If a woman dies due to infection prior to the 24-hour repeat sample, this death will be assumed to have been preceded by sepsis and will also be attributed as a sepsis related death. There is the potential for some women to be discharged prior to their Day 1 assessment. If this occurs, they will lack a reference standard at this timepoint and so will not be included in the primary analysis. However, these women with early discharge will be included in a sensitivity analysis which assumes that they were discharged because they were well and therefore did not have sepsis.

For the secondary outcome exploring if Day 0 venous lactate in addition to vital signs, improves prediction of severe morbidity and mortality from infection, the reference standard is the WHO "severe maternal outcomes" (4) which comprises of maternal death and organ specific complications ("near misses") (see Appendix 2).

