5.4 OUTCOME DEFINITIONS

The primary outcomes are the absolute differences in sensitivity and specificity between pairs of index tests: vital signs (Day 0) vs vital signs (Day 0) + lactate (Day 0), and vital signs (Day 0) + lactate (Day 0) vs vital signs (Day 0 and Day 1) + lactate (Day 0 and Day 1).

Secondary outcomes include:

- The absolute differences in sensitivity and specificity between vital signs (Day 0) alone and vital signs (Day 0) + lactate (Day 0) for maternal sepsis assessed at Day 0 only;
- The predictive value of vital signs (Day 0) alone compared to that of vital signs (Day 0) + lactate (Day 0) in those without sepsis at baseline, for maternal sepsis assessed at Day 1 only;
- The predictive value of vital signs (Day 0) alone compared to that of vital signs (Day 0) + lactate (Day 0) for the occurrence of severe morbidity and mortality from infection (WHO "severe maternal outcomes") (4), which is assessed daily until day 14 or discharge or death, if sooner;
- The sensitivity and specificity of vital signs (Day 0) + lactate (Day 0) and vital signs (Day 0 and Day 1) + lactate (Day 0 and Day 1) by: pregnancy status (pregnant or postdelivery/post miscarriage/post-abortion), source of sepsis (genital tract or nongenital tract) and condition on admission (stable or critical);
- The sensitivity and specificity of the primary index test comparisons including those women discharged early, assuming that they did not have sepsis;
- In an exploratory analysis, the sensitivity and specificity of each index test will be estimated based on different threshold values for lactate;
- To explore the use of an alternative reference standard, in which the SOFA score is modified to use maternity specific ranges for creatinine and platelet concentration, an independent expert review group will examine all cases with discordant results to adjudicate based on clinical features, clinical management, response to treatment and outcomes, if the case fitted the WHO definition of maternal sepsis. The pattern of discrepant results will be investigated descriptively.
 - 5.5 SAMPLE SIZE

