7.3 FINAL ANALYSIS

Primary analysis

We will estimate the sensitivity, specificity, positive predictive value (PPV) and negative predictive value (NPV) of the three index tests to detect sepsis assessed at Day 0 and Day 1. The 95% CIs for the estimates will be calculated using the Wilson method for proportions. To compare the accuracy of sepsis diagnosis by vital signs alone versus vital signs + lactate, we will fit separate generalized estimating equation (GEE) models for women with and without sepsis to estimate absolute differences in sensitivity and specificity, respectively. This approach exploits the paired nature of the data. We will compute absolute differences

in sensitivities and specificities from the GEE models using a post-estimation procedure with Cls computed using the delta method.

Secondary analyses

We will assess (a) index tests based on Day 0 only against Day 0 reference standard to determine immediate diagnostic value; (b) index tests based on Day 0 only against Day 1 reference standard in those without sepsis at baseline to determine short-term predictive value; and (c) index tests based on Day 0 only with occurrence of infection related "severe maternal outcome" (near miss or maternal mortality) (4) prior to hospital discharge to determine predictive value for severe morbidity or mortality (5) assuming that those women discharged prior to the Day 1 assessment did not have sepsis. Sensitivity, specificity, PPV, and NPV will be calculated for each test. In addition, for each of the analyses above, we will estimate absolute differences in sensitivity and specificity of vital signs alone versus vital signs (Day 0) + lactate (Day 0).

Pre-specified subgroup analyses will include pregnancy status (pregnant or postnatal) and illness severity to explore if the test accuracy of lactate in addition to vital signs alone varies by these subgroups.

Exploratory receiver operating characteristic (ROC) curve analyses will examine the effect of adjusting the threshold value for lactate on the sensitivity and specificity of the index tests.

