Appendix 2: Maternal "near misses"

Status
Brain conditions
Unconscious for more than 12 hours
Stroke
Status epilepticus or uncontrolled fits
Clotting and bleeding
Failure to form clots (clinically absence of clotting from an IV site or suture after 7
minutes, or bedside clotting test taking more than 7 minutes)
Transfusion of more than 2 units of blood
Platelets of less than 50*10^3/µL
Heart conditions
Cardiac arrest
Cardiopulmonary resuscitation
Shock (persistent systolic blood pressure less than 80mmHg with pulse more than
120 beats per minute)
Use of continuous vasoactive drugs e.g. adrenaline infusion
Kidney conditions
Oliguria (urine output less than 30ml/h for 4 hours or less than 400ml/24 hours) not responsive to fluids
Creatinine greater than 300 $\mu mol/L$ or 3.5mg/dL
Dialysis
Liver conditions
Bilirubin more than 100 µmol/L or 6.0 mg/dL
Lung conditions
Cyanosis
Gasping
Respiratory rate more than 40 or less than 6 breaths per minute
Low oxygen saturations of less than 90%% for more than 1 hour
Need for ventilation (not due to anaesthesia)
Uterus conditions
Laparotomy other than for caesarean section or ectopic pregnancy
Hysterectomy due to infection or haemorrhage
Uterine rupture

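### Severe-outcome analysis (c): the aim and SAP 7.3 are limited to infection, the reference standard in 5.3 and Appendix 2 is not, and women who already have the outcome at Day 0 are not set apart

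*SAP*

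**What the plan says.** **Aim.** SAP 3 lists, as a secondary objective, whether baseline lactate improves prediction of severe morbidity and mortality from infection.

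**Reference standard.** SAP 5.3 repeats the aim and fixes the standard in one sentence: lactate "improves prediction of severe morbidity and mortality from infection, the reference standard is the WHO" severe maternal outcome, "which comprises of maternal death and organ specific complications". It refers to Appendix 2 for the list. The definition carries no restriction by cause. Appendix 2 includes "Hysterectomy due to infection or haemorrhage", "Uterine rupture" and transfusion of more than 2 units with no cause attached.

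**Outcome.** SAP 5.4 compares the tests "for the occurrence of severe morbidity and mortality from infection" and gives the WHO outcome in brackets as if the two were the same. Assessment is daily to day 14, or to discharge or death if sooner.

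**Analysis.** SAP 7.3, analysis (c), relates "index tests based on Day 0 only with occurrence of infection related" severe maternal outcome before hospital discharge. No day 14 limit is stated.

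**Timing.** Appendix 1 schedules the near-miss assessment from Day 0. SAP 4.2 admits women who already have organ dysfunction, and women having "Any procedure for treatment of a suspected infection (e.g., wound exploration, evacuation of the uterus, laparotomy, etc". Appendix 2 also counts laparotomy, other than for caesarean section or ectopic pregnancy. Analysis (b) is confined to women without sepsis at baseline. Analysis (c) has no matching restriction.

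**The concern.** There are two problems, and both bear on who counts as a case in (c).

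First, the stated aim and the operational definition do not match. An analyst who works from 5.3 and Appendix 2 counts every listed event and every maternal death. An analyst who works from 7.3 drops those not related to infection. Sensitivity, specificity, PPV and NPV can all differ between the two, and the choice could be made after the data are seen.

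Second, a criterion already met when the Day 0 tests are taken is not predicted by them. Some Appendix 2 criteria are more extreme forms of the vital signs in Table 1, so in those women the vital-sign test is positive by construction. The comparison of tests in (c) then mixes detection of a present state with prediction of a later one.

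**Working it through.** The SAP gives no event rate, power or sample size for (c), so there is no figure to reproduce. The sample size in 5.5 concerns sepsis.

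**1. Case status under each section**

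| Woman's only event | 5.3 with Appendix 2 | 7.3 |
|---|---|---|
| Near miss due to infection | case | case |
| Uterine rupture unrelated to infection | case | non-case |
| Hysterectomy due to haemorrhage | case | non-case |
| Transfusion of more than 2 units for a non-infective cause | case | non-case |
| Maternal death from another cause | case | non-case |

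The last four rows move between the sensitivity denominator and the specificity denominator.

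**2. Illustration of the first problem (all values assumed except N = 500 from SAP 5.5)**

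Let r be the infection-related outcome rate (5% to 20%) and f the share of all listed events that are not infection-related (10% to 40%).

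- Events under 7.3 = N × r: 500 × 0.05 = 25 to 500 × 0.20 = 100.
- Events under 5.3 = N × r / (1 − f): 25 / 0.9 ≈ 28 to 100 / 0.6 ≈ 167.

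Sensitivity under the all-cause endpoint = (1 − f) × Se(infection) + f × Se(other). With Se(infection) = 0.70:

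- Se(other) = 0.30: 0.9 × 0.70 + 0.1 × 0.30 = 0.66; 0.6 × 0.70 + 0.4 × 0.30 = 0.54.
- Se(other) = 0.70: 0.70 throughout.
- Se(other) = 0.90: 0.9 × 0.70 + 0.1 × 0.90 = 0.72; 0.6 × 0.70 + 0.4 × 0.90 = 0.78.

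SAP 7.3 also compares tests. Under the rule in 5.2 that both components must be positive, the loss in sensitivity from adding lactate is v × (1 − l), where v is vital-sign sensitivity and l is the share of vital-sign-positive cases with raised lactate. Take l = 0.6 in both kinds of event. The loss is 0.70 × 0.4 = 28.0 points under the infection endpoint. Under the all-cause endpoint it lies between 0.54 × 0.4 = 21.6 and 0.78 × 0.4 = 31.2 points. The direction is open for both quantities.

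**3. Overlap at Day 0 (Appendix 2 against Table 1)**

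- Shock: systolic pressure below 80 with pulse above 120 meets both below 90 and above 120.
- Respiratory rate above 40 meets above 25.
- Unconsciousness implies an altered mental state.
- Oliguria below 30 ml/h does not always imply a positive sign: 30 / 0.5 = 60 kg, so the implication depends on weight.
- Respiratory rate below 6 has no counterpart in Table 1.

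Let g be the share of counted events that are of the first three kinds and present at the Day 0 measurement. Vital-sign sensitivity in that group is 1 by construction, so overall it is g + (1 − g) × v. With v = 0.70 assumed for later events, g = 10% gives 0.10 + 0.90 × 0.70 = 0.73, and g = 40% gives 0.40 + 0.60 × 0.70 = 0.82.

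The combined test can never be more sensitive than vital signs alone, in any woman. In this group the loss from adding lactate is simply the share whose lactate is not raised, 1 − l0. The overall loss is g × (1 − l0) + (1 − g) × v × (1 − l1), where l1 applies to later events. With v = 0.70 and l1 = 0.6, the loss without such women is 28.0 points. At g = 40% it is:

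- l0 = 0.6: 0.4 × 0.4 + 0.6 × 0.28 = 0.328, or 32.8 points.
- l0 = 1: 0 + 0.6 × 0.28 = 0.168, or 16.8 points.

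So the vital-sign sensitivity rises in this example, but the paired difference can move either way.

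**The case against.** The strongest reply is that the SAP has one endpoint. The restriction to infection appears in 3, 5.3, 5.4 and 7.3, so Appendix 2 can be read as a list of criteria to be applied to infection-related events. How an event is attributed to infection may sit in the protocol or on the near-miss form, neither of which is shown. Part of this stands: the mismatch lies between the aim and its operational definition, including within 5.3 itself, and the absence of an attribution rule is not by itself the finding. But 5.3 states what the reference standard is, and Appendix 2 expressly accepts haemorrhage as a cause of hysterectomy. The SAP's own wording supports both readings.

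Three stronger readings are tempting, and the document does not support them.

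- A reader might infer that obstetric haemorrhage is scored as an infection outcome. It is not a listed near miss; it appears only as a reason for hysterectomy, and transfusion is listed without a cause.
- A reader might infer that non-infective events must dilute sensitivity. That holds only if the tests are positive less often in such events, which the SAP does not tell us.
- A reader might infer that the overlap favours vital signs over lactate. No lactate-alone test exists; vital signs are part of both tests compared in (c), and the effect on their difference depends on how often lactate is raised in these women.

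It is also fair that this is one secondary objective, worded as exploratory.

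**Conclusion.** The point holds in limited form. For (c), case status depends on whether 5.3 with Appendix 2 or 7.3 is followed, and the analysis as written can count outcomes already present when the index tests are taken. Where such a state is shock, a respiratory rate above 40 or unconsciousness at the Day 0 measurement, the result is not prediction. The window also differs between 5.4 and 7.3, which matters for women still in hospital after day 14.

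The size cannot be derived from the SAP. The illustrations rest on assumed event rates, assumed shares of non-infective and Day 0 events, and assumed sensitivities; they show only that the results could change materially and in either direction. The primary analysis and the sample size do not depend on this point. It should be corrected before the data are analysed.

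**What to change.** - State one endpoint in the same words in 5.3, 5.4 and 7.3. The natural choice, given the aim, is infection-related death or near miss, with an attribution rule fixed before analysis and applied blind to lactate, using data already recorded. Report the all-cause WHO outcome as a sensitivity analysis.
- Nothing in the SAP shows that the near-miss form records cause. If it does not, make the all-cause outcome the endpoint and reword the aim and 7.3 to match.
- Count only deaths and criteria first met after the Day 0 index measurement. Tabulate women who already meet a criterion at Day 0 separately, in line with how (b) treats sepsis at baseline. Say how a Day 0 criterion is classified if it cannot be timed against the measurement.
- Use one window, choosing between day 14 and hospital discharge in 5.4 and 7.3.

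The cost is mainly SAP wording, with some record review if attribution is needed. The real downside is fewer events and wider intervals in (c), possibly by more than a little if many women meet a criterion at entry. No new data collection is implied.

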5.4 OUTCOME DEFINITIONS

The primary outcomes are the absolute differences in sensitivity and specificity between pairs of index tests: vital signs (Day 0) vs vital signs (Day 0) + lactate (Day 0), and vital signs (Day 0) + lactate (Day 0) vs vital signs (Day 0 and Day 1) + lactate (Day 0 and Day 1).

Secondary outcomes include:

- The absolute differences in sensitivity and specificity between vital signs (Day 0) alone and vital signs (Day 0) + lactate (Day 0) for maternal sepsis assessed at Day 0 only;
- The predictive value of vital signs (Day 0) alone compared to that of vital signs (Day 0) + lactate (Day 0) in those without sepsis at baseline, for maternal sepsis assessed at Day 1 only;
- The predictive value of vital signs (Day 0) alone compared to that of vital signs (Day 0) + lactate (Day 0) for the occurrence of severe morbidity and mortality from infection (WHO "severe maternal outcomes") (4), which is assessed daily until day 14 or discharge or death, if sooner;
- The sensitivity and specificity of vital signs (Day 0) + lactate (Day 0) and vital signs (Day 0 and Day 1) + lactate (Day 0 and Day 1) by: pregnancy status (pregnant or postdelivery/post miscarriage/post-abortion), source of sepsis (genital tract or nongenital tract) and condition on admission (stable or critical);
- The sensitivity and specificity of the primary index test comparisons including those women discharged early, assuming that they did not have sepsis;
- In an exploratory analysis, the sensitivity and specificity of each index test will be estimated based on different threshold values for lactate;
- To explore the use of an alternative reference standard, in which the SOFA score is modified to use maternity specific ranges for creatinine and platelet concentration, an independent expert review group will examine all cases with discordant results to adjudicate based on clinical features, clinical management, response to treatment and outcomes, if the case fitted the WHO definition of maternal sepsis. The pattern of discrepant results will be investigated descriptively.
 - 5.5 SAMPLE SIZE

We aim to recruit 500 women to the study in total. In computing sample sizes, we estimated that an increase of 20% in sensitivity would be both feasible and clinically important. This equates to detecting an additional sepsis case for every 5 women who have sepsis. Assuming a prevalence of 40%, defining statistical significance at the 5% level and ensuring 90% power, up to 346 participants in total would ensure we are appropriately powered across a range of baseline sensitivities between 30 and 60% when vital signs alone are used. It is important to also estimate specificity to detect any important increase in false positives. With 200 patients without sepsis, the specificity of each test will be estimated with 95% confidence interval (CI) width of 15 percentage points for a specificity of 75% and width less than 10 percentage points for a specificity of 90%. This is adequate precision to allow important changes to be estimated. Allowing for loss to follow-up and missing / laboratory results, we consider an initial sample size of 500 as appropriate to allow the study to have adequate power to test these hypotheses. This number of cases will be feasible to collect within 12 months, based on current infection rate data from all sites.

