3 OBJECTIVES

The primary objective is to evaluate the diagnostic accuracy of maternal venous lactate measurement in addition to maternal vital signs (at Day 0 and/or Day 1), in maternal sepsis in low-resource health facility settings in Malawi, Uganda and Pakistan.

Secondary objectives are to:

• evaluate the immediate diagnostic value of lactate testing at Day 0 in addition to maternal vital signs in maternal sepsis at Day 0 (reference standard at Day 0 only);

- assess the short-term predictive value of lactate testing at baseline, in addition to vital signs, for maternal sepsis at 24-hours (24-hour reference standard) in those without sepsis at baseline;
- explore if baseline venous lactate, in addition to vital signs, improves prediction of severe morbidity and mortality from infection;
- explore if the diagnostic accuracy of lactate in addition to maternal vital signs alone, varies by the pre-specified subgroups of pregnancy status (pregnant or post-delivery / post miscarriage / post-abortion), source of sepsis (genital tract or non-genital tract) and condition on admission (stable or critical);
- examine the effect of adjusting the threshold values for lactate assessment on the sensitivity and specificity of the index tests;
- explore the use of an alternative reference standard in which the Sequential Organ Failure Assessment (SOFA) score is modified to use maternity specific ranges for creatinine and platelet concentration.

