5.2 INDEX TESTS

The three index tests being evaluated are:

- 1) Vital signs at Day 0 (see Table 1)
- 2) Vital signs at Day 0 + lactate at Day 0
- 3) Vital signs at Day 0 and Day 1 + lactate at Day 0 and Day 1

The vital signs will indicate sepsis if one or more of the thresholds listed in Table 1 are exceeded. A lactate >2mmol/L will indicate sepsis. For tests combining vital signs and lactate, both will need to indicate sepsis to give a positive test result. For the test combining Day 0 and Day 1 measurements, a positive test will require the vital signs and lactate measurements to indicate sepsis at either Day 0 or Day 1.

Vital sign	Threshold
Respiratory Rate	>25 per minute
Heart rate	>120 beats per minute
Systolic Blood Pressure	< 90mmHg
Urine output	Less than 0.5ml/kg/hour
Mental state	Altered state

Table 1: Vital sign threshold values

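### The second primary comparison measures the effect of repeating the whole assessment, not of lactate, and no two-day vital-signs test without lactate exists to isolate lactate over both days

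*SAP*

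**What the plan says.** The primary objective in SAP section 3 is to "evaluate the diagnostic accuracy of maternal venous lactate measurement in addition to maternal vital signs (at Day 0 and/or Day 1").

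Section 5.2 lists three index tests:

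- Test 1: vital signs at Day 0. This is the only test without lactate.
- Test 2: vital signs and lactate, both at Day 0.
- Test 3: vital signs and lactate at both Day 0 and Day 1.

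Where vital signs and lactate are combined, "both will need to indicate sepsis to give a positive test result". For test 3, "a positive test will require the vital signs and lactate measurements to indicate sepsis at either Day 0 or Day 1".

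Section 5.4 names two primary comparisons: test 1 with test 2, and test 2 with test 3 ("vital signs (Day 0) + lactate (Day 0) vs vital signs (Day 0 and Day 1) + lactate (Day 0 and Day 1"). Section 7.3 describes only one kind of contrast: "To compare the accuracy of sepsis diagnosis by vital signs alone versus vital signs + lactate".

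In the primary analysis all three tests face the same reference standard. Section 5.3 says: "Women will be diagnosed as having sepsis if they meet the criteria at either time point".

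**The concern.** The objective asks what lactate adds to vital signs, at Day 0 and/or Day 1. A contrast that answers this must hold the vital-sign information fixed and change only lactate. Test 1 versus test 2 does so at Day 0. Test 2 versus test 3 does not: moving from one to the other adds a Day 1 vital-sign assessment and a Day 1 lactate together.

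Two things raise the risk of misreading. Because vital signs and lactate must both be positive, adding lactate in the first comparison can only lower sensitivity or leave it unchanged. The second comparison is therefore the only primary one in which a sensitivity gain can appear. The sample size in section 5.5 is built around a 20-point gain in sensitivity over vital signs alone, so readers will look for such a gain and may credit lactate with one that came from looking twice.

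**Working it through.** **What follows from the definitions alone.** Write V0, V1 for positive vital signs and L0, L1 for positive lactate on Day 0 and Day 1.

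- Test 2 = V0 and L0.
- Test 3 = (V0 and L0) or (V1 and L1), taking the same-day reading.
- Two-day vital signs (not in the SAP) = V0 or V1.

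Test 2 positives are a subset of test 3 positives. So, whatever lactate measures:

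- sensitivity(3) − sensitivity(2) = P(positive on Day 1 only | sepsis) ≥ 0
- specificity(3) − specificity(2) = −P(positive on Day 1 only | no sepsis) ≤ 0

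The sensitivity difference is strictly positive once one woman with sepsis is positive on Day 1 only.

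**How large this can be.** The SAP gives no figure for this comparison, so there is none to reproduce. The inputs below are assumptions; of these quantities, only the range of 30–60% for the baseline sensitivity of vital signs (section 5.5) is in the SAP.

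- Vital signs on each day: sensitivity 60%, specificity 80%.
- Lactate: positive in 50% of women on each day, regardless of sepsis and vital signs, so it carries no information.
- Latent between-day correlation (bivariate normal) 0.5, for vital signs and for lactate.

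These imply the following probabilities of being positive on both days: vital signs 0.4391 with sepsis and 0.0872 without; lactate 0.3333.

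With p the daily probability of positive vital signs in the group, q = 0.50, and V11 and L11 the both-day probabilities:

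- Test 2 positive = p·q
- Test 3 positive = 2·p·q − V11·L11
- Two-day vital signs positive = 2·p − V11

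With sepsis (sensitivity):

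- Test 2: 0.60 × 0.50 = 30.0%
- Test 3: 0.60 − 0.4391 × 0.3333 = 45.4%
- Two-day vital signs: 1.20 − 0.4391 = 76.1%

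Without sepsis (specificity):

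- Test 2: 1 − 0.20 × 0.50 = 90.0%
- Test 3: 1 − (0.20 − 0.0872 × 0.3333) = 82.9%
- Two-day vital signs: 1 − (0.40 − 0.0872) = 68.7%

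| Contrast | Sensitivity difference | Specificity difference |
|---|---|---|
| Test 3 − test 2 (in the SAP) | +15.4 points | −7.1 points |
| Test 3 − two-day vital signs (not in the SAP) | −30.7 points | +14.2 points |

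The same uninformative lactate shows opposite signs, depending on whether the second day of vital signs is held fixed.

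**Range.** The assumptions were varied over 36 scenarios by simulation: vital-sign sensitivity 30%, 45% or 60%; uninformative lactate positive in 20%, 40%, 60% or 100%; correlation 0, 0.5 or 0.8. The sensitivity gain of test 3 over test 2 ran from 3.3 to 24.8 points. With a 25% daily false-positive rate for vital signs, the specificity loss ran from 2.8 to 18.8 points. Against two-day vital signs, the sensitivity difference of test 3 lay between −61.4 and 0 points.

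**Same-day or cross-day.** The positivity sentence for test 3 does not say that both components must be positive on the same day. If vital signs on one day and lactate on the other also counted, test 3 would be positive with probability (2·p − V11) × (2·q − L11). In the illustration this gives sensitivity 0.7609 × 0.6667 = 50.7% and specificity 1 − 0.3128 × 0.6667 = 79.1%, against 45.4% and 82.9% on the same-day reading.

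**The case against.** Several points on the other side stand.

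- Section 5.4 labels the second comparison by its full content. Whether one combined assessment or two is better is a legitimate question, and the SAP nowhere calls the answer the value of repeat lactate.
- Test 1 versus test 2 isolates lactate at Day 0, and the secondary accuracy comparisons against the Day 0, Day 1 and severe-outcome reference standards use that same contrast. A reader might infer that the primary objective as a whole cannot be answered. The document does not support that: only the Day 1 part lacks a contrast.
- A reader might also infer that a worthless lactate test is certain to look beneficial. The definitions guarantee only that sensitivity does not fall; a gain needs at least one woman with sepsis who is positive on Day 1 only. Specificity belongs to the same primary outcome, so the loss would be reported beside the gain.
- The missing contrast is one-directional too. Test 3 positives are a subset of two-day vital-sign positives, so sensitivity can only fall and specificity can only rise. One-directional differences are therefore not in themselves the defect, and they give no reason to drop or demote test 2 versus test 3.
- The natural reading of the test 3 rule is same-day, so that point is a minor clarification.

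What remains is the confounding of day with lactate. Reporting specificity does not resolve it: a gain in sensitivity with a loss in specificity cannot show whether the second vital signs or the second lactate produced it.

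**Conclusion.** The point holds in a limited form. Test 2 versus test 3 estimates the effect of repeating the combined assessment. It cannot be read as the added value of lactate, and the Day 1 part of the primary objective has no contrast that isolates lactate.

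The direction rests only on the SAP's definitions. The size is illustrative: +15.4 points of sensitivity and −7.1 points of specificity in the worked case, and 3.3 to 24.8 points of sensitivity gain across the scenarios. All of these assume lactate positivity, vital-sign specificity and between-day correlations that the SAP does not give. The Day 0 primary comparison is unaffected. No data are lost, because Appendix 1 schedules vital signs on both days. It is an inexpensive improvement that lets the trial answer its own question.

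**What to change.** - **Section 5.2:** add a fourth index test, vital signs at Day 0 and Day 1, positive if any Table 1 threshold is met on either day. State that for test 3 vital signs and lactate must both be positive on the same day.
- **Sections 5.4 and 7.3:** add the paired comparison of this new test with test 3. Report the sensitivity and specificity differences together, since under the both-positive rule the first can only fall and the second can only rise.
- **Sections 5.4 and 7.3:** keep test 2 versus test 3, name it explicitly in 7.3, and state that it measures repeat testing and is not to be read as the effect of lactate.

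The cost is one derived variable, the SAP wording and one more comparison to report. No new data are needed. As this touches the primary outcomes, any matching wording in the protocol, which was not available here, should be checked for consistency.
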